## A Randomized, Controlled Trial Comparing Telehealth Self-Management to Heart Failure Clinic Outpatient Management in Black and Hispanic Disparity Patients Living with Heart Failure

[name], [name], MA, [name], [name], [name], [name], NP, [name], MS, [name], [name], [name], LMSW, [name], MSN, [name], and [name], MPH

The health system's Biostatistics Unit created a randomization schedule for patient assignment, to randomize patients to either TSM or COM using permuted block randomization, with stratification by heart class, to ensure equal representation of heart class across the two groups. The primary analysis of this randomized clinical trial was based on intention to treat (ITT) principle, which included all subjects randomized. Descriptive statistics are presented as means, standard deviations, medians, ranges and frequency/percentages.

Inpatient utilization was defined in three ways, including: 1) whether an individual patient had at least one inpatient hospitalization over the 90 day period; 2) the number of hospitalizations experienced by an individual patient over the 90 day period; and 3) the cumulative length of stay (LOS) (inpatient days) experienced by an individual patient

over the 90 day period (i.e., for multiple hospitalizations, the sum of all LOS's was computed as the cumulative LOS).

ED utilization was defined as whether or not an individual patient had at least one ED visit over the 90-day period. Binary outcomes for ED visits and hospitalizations were analyzed using the standard Chi-square or Fisher's exact test. Associated 95% confidence intervals for these proportions and their differences were computed using exact methods. The number of ED visits as well as hospitalizations within each group were separately compared using Poisson regression (SAS PROC GENMOD). Due to excess zeros (i.e., zero inflation), methods for over dispersed Poisson were required for both ED visits and hospitalizations. Cumulative LOS (inpatient days) was analyzed using a negative binomial regression. HF-related hospitalizations, ED visits, and LOS were analyzed in the same fashion described above, as were cardiovascular related outcomes. Reasons for ED visits as well as hospitalizations were classified as: HF alone (yes/no), cardiovascular related alone (yes/no), or both by the clinical team.

Repeated measures analysis of variance (RMANOVA) with a mixed models approach was used to compare changes at enrollment and at 90 days between groups. New York Heart Association (NYHA) class, PHQ-4, MLHFQ Physical and Emotional subscales were also analyzed using RMANOVA. The subscales of Anxiety and Depression, as measured by the PHQ-4, were dichotomized to presence or absence and Generalized Estimating Equations (GEE) were used to analyze these binary data. Days at home was

calculated as a proportion of days spent out of hospital during the 90 day period. The two groups were compared using the Mann-Whitney test.

Subgroup analyses included: patients hospitalized, heart class (2 vs. 3), and patients not receiving home care (prevalent in disparity populations). For the TSM group only, adherence was calculated, with low adherence defined as less than 10 vital signs uploads over the 90 day period.

Sample size and power calculations were based on previous literature and preliminary data from a non-disparity randomized RCT TSM study. We hypothesized that 75% of patients in the COM group would be hospitalized at least once during the study period and that TSM would reduce that rate to 50% (a relative reduction of 50%). The calculation was based on a chi-square test (alpha=0.05, two-tailed) with an n=52 patients per group. All analyses were performed using SAS 9.4 (SAS Institute Inc., Cary, NC).

The Northwell Health Institutional Review Board (IRB#13-518A) approved the study protocol.

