Upload compliance: We are arbitrarily defining three levels of compliance: High, moderate and minimal. "Minimal" compliance is defined as at least one upload per week for 6 out of the 12 weeks. "Moderate" compliance is defined as at least one upload per week for 9 out of the 12 weeks, and "High" compliance is defined as at least three uploads per week for 9 out of the 12 weeks. *A secondary compliance measure will be the number of uploads over* the 90 day period. = u/d. (maximum number of possible uploads = 90). All of these measures will be appropriately prorated for patients who die, or are hospitalized during the study, and are therefore not subject to uploading requirement during those times. With a sample size of 52 patients, the rates of compliance can be estimated to, at worst, +- 13.9%, with a 95% CI.

Total number of visits: We will compute the proportion of 12 scheduled visits that are kept. Therefore, if a patient is being followed for *w* weeks, there should be *w* scheduled visits. If the number scheduled visits that are kept is denoted by *v*, then the proportion of scheduled visits kept = v/w. Visit participation rates will be averaged across patients, and the mean rate will be computed, along with 95% confidence intervals. There is a maximum of 12 possible telehealth visits over the 3 month study period.

Patient satisfaction: We will measure patient perceptions of usability using a slightly modified version of the Telemedicine Satisfaction and Usefulness Questionnaire (Appendix 3). This 22-item questionnaire, which utilizes a 5 point Likert scale, will elicit a total sum score of satisfaction/usability that will then be dichotomized into satisfied vs. not satisfied based on previous literature.

Sample size considerations: We will randomize 116 patients as they are discharged from the hospital (58 per arm) in order to yield a maximum of 52 patients in the TSM arm of the study over a two year period.

These scores will be assessed using mean scores, percentages and histograms.²⁵ For satisfaction rates of 50%, 75% and 90%, with a sample size of 52, the corresponding 95% confidence intervals will have precision of +/- 13.9%, 12.7%, and 8.3%, .

Aim 2: we will measure inpatient utilization, emergency room utilization and QoL of patients receiving telehealth technology vs. standard of care patients.

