2a. Measures of Inpatient Utilization. Inpatient utilization will be measured in three ways, including: 2a.1) whether an individual subject had at least one inpatient hospitalization over the 3 month period; 2a.2) the number of hospitalizations experienced by an individual subject over the 3 month period; and 2a.3) cumulative length of stay (LOS) (inpatient days) experienced by an individual subject over the 3 month period (i.e., for multiple hospitalizations, the sum of all LOS's will be computed as the cumulative LOS). Cumulative LOS will be analyzed in two ways: intention to treat (ITT) analysis, and for only those hospitalized. The ITT analysis will include all patients, regardless of hospitalization history, to address the bigger public health issue: does TSM have an impact on LOS overall? A secondary analysis will look at LOS only for those who experienced a hospitalization. Finally, after ITT analysis, secondary analyses will include covariate adjustments for possible confounders.

Statistical Methods: Inpatient Utilization. For outcome 2a.1, the proportions of patients in each group who were hospitalized will be compared using the standard Chi-square or Fisher's exact test. Associated 95% confidence intervals for these proportions and their differences will be computed using exact methods. For outcome 2a.2, the number of hospitalizations will be compared using Poisson regression (SAS PROC GENMOD). It is likely that, due to excess zeros (i.e., zero inflation), methods for overdispersed Poisson will be required. Another approach for both outcomes 2a.2 and 2a.3 will be to use Lachenbruch's two stage procedure for zero-inflated data.30 For these primary ITT analyses, no adjustments will be made for any covariates.

Sample size considerations: We expect to enroll 52 patients in the TSM group which will yield the necessary statistical power.

2b. Measures of ER Utilization, defined as: 2b.1) whether or not an individual subject had at least one ER visit over the 3 month period; and 2b.2) the number of ER visits experienced by an individual subject over the 3 month period. Covariate adjustments will be made for potential confounders.

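### The hospitalization, ED-visit and inpatient-day models carry no offset for observed follow-up, so unobserved time after withdrawal or loss to contact is implicitly treated as event-free

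*SAP*

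**What the plan says.** The SAP defines the hospitalization outcome as "the number of hospitalizations experienced by an individual patient over the 90 day period", and cumulative inpatient days over the same window. On the analysis set it says: "The primary analysis of this randomized clinical trial was based on intention to treat (ITT) principle, which included all subjects randomized". For the models it says "The number of ED visits as well as hospitalizations within each group were separately compared using Poisson regression (SAS PROC GENMOD", adds that "Due to excess zeros (i.e., zero inflation), methods for over dispersed Poisson were required for both ED visits and hospitalizations", and for inpatient days states that "Cumulative LOS (inpatient days) was analyzed using a negative binomial regression".

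The protocol's Aim 2 methods are of the same kind: "For outcome 2a.2, the number of hospitalizations will be compared using Poisson regression (SAS PROC GENMOD", with a similar approach for ER visits. Neither document mentions an offset, person-time, censoring, or a rule for death or withdrawal in these outcomes.

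Other parts of the protocol show that incomplete follow-up is possible:

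- The section on discontinuation allows withdrawal at any time.
- Table 1 records death in both arms.
- Under Aim 1, "We will randomize 116 patients as they are discharged from the hospital (58 per arm" in order to reach at most 52 in the TSM arm.
- Upload compliance is adjusted for time when uploading is not required: "All of these measures will be appropriately prorated for patients who die, or are hospitalized during the study". Visit participation is divided by the weeks a patient was actually followed.

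**The concern.** Table 1 labels ER use and hospitalizations as primary outcome variables. It lists them under the weekly visit (video for TSM, phone for control), and the standard-of-care section says control patients are asked about them at the weekly contact. The documents describe no capture from records once contact stops. A patient who leaves on day 20 therefore has 20 observed days, but a count model without an offset takes that count as the 90-day total.

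The treatment comparison suffers only if the arms lose different amounts of time. That is possible here because the burden differs: TSM patients must accept equipment at home and transmit readings daily, while control patients receive a weekly call. If time is lost unevenly, part of the estimated utilization ratio reflects how long patients were watched and not how often they were admitted.

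**Working it through.** **Plan's own figure.** There is none to reproduce. The SAP's sample size (52 per group, 75% vs 50%) concerns the binary hospitalization outcome and has no bearing on the offset. The documents give no exit rate by arm, so every exit rate below is an assumption. The figure of 10.3% is simply (58 − 52)/58 = 6/58, used as a convenient size.

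**Formula.** Suppose exit is unrelated to a patient's event rate. The expected observed count is then the event rate times the mean share of the 90 days observed. A model without an offset therefore estimates

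apparent ratio = true ratio × (mean share observed, TSM) / (mean share observed, control),

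where mean share observed = 1 − (proportion exiting) × (average share of follow-up lost by those who exit). Uniform exit times give an average loss of 0.5.

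**Results with a true ratio of 1.00:**

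| Exits, TSM / control | Share lost by leavers | Calculation | Apparent ratio |
|---|---|---|---|
| 10.3% / 10.3% | 0.5 | 0.949 / 0.949 | 1.000 |
| 10.3% / 0% | 0.5 | 0.949 / 1.000 | 0.949 |
| 0% / 10.3% | 0.5 | 1.000 / 0.949 | 1.054 |
| 15% / 5% | 0.5 | 0.925 / 0.975 | 0.949 |
| 20% / 5% | 0.5 | 0.900 / 0.975 | 0.923 |
| 5% / 20% | 0.5 | 0.975 / 0.900 | 1.083 |
| 20% / 5% | 0.75 | 0.850 / 0.9625 | 0.883 |

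**Simulation check.** Overdispersed Poisson models were fitted with and without a log(time) offset. Settings were 52 per arm, 1,500 runs, uniform exit times, an assumed gamma variance of 0.5, and a control mean of 1.386 events. That mean is −ln(1 − 0.75), taken from the SAP's 75% control rate under a plain Poisson. The true ratio was 1.00.

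| Exits, TSM / control | No offset: ratio, rejection rate | Offset: ratio, rejection rate |
|---|---|---|
| 10.3% / 10.3% | 0.995, 3.9% | 0.995, 4.3% |
| 20% / 5% | 0.916, 7.8% | 0.993, 5.7% |
| 30% / 5% | 0.875, 8.2% | 1.004, 5.5% |

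The Monte Carlo standard error of a 5% rejection rate is √(0.05 × 0.95 / 1,500) = 0.6 percentage points. The offset removes the bias when exit is unequal and changes almost nothing when it is equal.

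**Death is a different case.** After withdrawal, later events are unobserved. After death, no further admissions is the true count. An offset for days alive would turn total 90-day use into a rate while alive. For example, 8 inpatient days in a patient who dies on day 10 would become 8/10 × 90 = 72 days per 90.

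**The case against.** The strongest reply is that total utilization over 90 days in all randomized patients is a legitimate intention-to-treat quantity, and the protocol presents length of stay overall as the broader public health question. This stands for deaths: a days-alive offset would change the estimand and would not correct an error. It does not cover withdrawals, where the 90-day total is unknown and the model would take a partial count as complete.

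Several stronger readings are tempting, and the documents do not support them:

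- *That early leavers are scored as fully observed and event-free.* The documents do not say how leavers are scored, and events before exit would still be counted. Only the time after exit is implicitly event-free.
- *That the plan expects about 10% loss.* The 58 and the 52 are stated, but no attrition rate or cause is. Some of the gap could be refusal of installation, which need not end utilization follow-up.
- *That the bias must favour TSM.* It reverses if control loses more time, and equal loss produces none.
- *That the proration sentence shows exit dates are already collected.* It covers TSM uploads only, and death and hospitalization only. It does not supply withdrawal dates or any control-arm dates.

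If utilization is in fact taken from hospital records for the full 90 days whatever the contact status, the withdrawal problem shrinks. The documents do not describe such capture.

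**Conclusion.** The concern holds as an omission with a concrete consequence. None of the three count models specifies an offset for observed follow-up, and no other part of the documents makes up for it. The rate ratio is unbiased when the arms are followed equally, although both absolute rates are then understated. With unequal follow-up, the shift is about 5% when 10.3% exit in one arm only, and about 8% with 20% against 5%, at uniform exit times. It reaches about 12% in the latter case if leavers lose three quarters of their follow-up. The effect on the rejection rate is modest: 7.8% against 5.7% in the 20% / 5% simulation.

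These sizes rest on assumed exit rates, on exit unrelated to event rate, and on events being unobserved after contact ends. The direction cannot be predicted from the documents.

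**What to change.** 1. Add log(days of observed follow-up, up to 90) as an offset in the Poisson models for hospitalizations and ED visits and in the negative binomial model for inpatient days. Censor time at withdrawal or loss to contact, dated from the weekly contacts in both arms. State how patients with no contact after randomization are counted, since log(0) is undefined.
2. Treat death separately. In the main analysis keep total 90-day utilization, with death as a true end of events, so that a patient who dies under observation has a complete 90-day count. Add an offset for days alive and observed as a sensitivity analysis.
3. Report deaths, withdrawals and mean follow-up by arm.

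The cost is one model option, the derivation of last-contact dates to about a week's precision, one extra analysis and a few sentences in the SAP. Two limits remain. The offset assumes that withdrawal is non-informative. It also does nothing for the binary outcomes (any hospitalization, any ED visit), which incomplete follow-up affects too and which need their own rule.

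### Days at home has no rule for death: under either natural reading an early death without admission scores 100% and ties with the best outcome.

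*SAP*

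**What the plan says.** The whole definition is one clause in the SAP's statistical methods: days at home was "calculated as a proportion of days spent out of hospital during the 90 day period". The next sentence gives the test: "The two groups were compared using the Mann-Whitney test". Nothing says that only days alive count, what the denominator is for a patient who dies, or what happens to a patient lost to follow-up.

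Four other places bear on it:

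- The SAP describes the primary analysis as intention to treat, "which included all subjects randomized". Nothing removes patients who die from the days-at-home comparison.
- Cumulative LOS is a plain sum ("for multiple hospitalizations, the sum of all LOS's was computed as the cumulative LOS"), also without a death rule.
- Table 1 of the protocol records death in both arms, so deaths were foreseen.
- The protocol deals with incomplete time for two other measures, both under Aim 1 of its statistical section. For uploads: "All of these measures will be appropriately prorated for patients who die, or are hospitalized during the study". For visits, the denominator is the number of weeks followed: "then the proportion of scheduled visits kept = v/w". Neither rule is extended to days at home, which the protocol does not list as an outcome.

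**The concern.** A reader will take days at home as a measure of patient benefit: more is better. As defined, the score falls only when a patient is in hospital. A patient who dies at home soon after discharge has no inpatient days and gets the maximum. In a rank test that patient shares the top rank with survivors who were never admitted.

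The participants have just been in hospital for heart failure, and the protocol's background calls the disease a leading cause of death. If one arm had more deaths, this outcome would largely fail to show it. Because death also ends the time in which a patient can be admitted, the outcome could drift in that arm's favour.

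**Working it through.** The documents state no expected value, power or death rate for days at home, so there is no figure to reproduce. The check applies the definition to individual patients and then to assumed death rates.

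**Step 1: single patients.** Let t be the day of death (90 for a survivor) and L the inpatient days.

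- A, literal: (90 - L)/90
- B, days alive as denominator: (t - L)/t
- C, days alive and out of hospital over 90: (t - L)/90

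| t | L | A | B | C |
|---|---|---|---|---|
| 10 | 0 | 90/90 = 100% | 10/10 = 100% | 10/90 = 11.1% |
| 30 | 0 | 100% | 100% | 33.3% |
| 30 | 5 | 85/90 = 94.4% | 25/30 = 83.3% | 25/90 = 27.8% |
| 10 | 5 | 94.4% | 5/10 = 50.0% | 5/90 = 5.6% |
| 90 | 5 | 94.4% | 94.4% | 94.4% |

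A and B differ for patients admitted before death but agree at 100% for those who were not. Only C separates an early death from a survivor who was never admitted. Survivors score the same under all three.

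**Step 2: what 100% means in ranks.** The SAP plans for 75% hospitalized under COM and 50% under TSM, "with an n=52 patients per group". On those rates, 0.25 x 52 = 13 COM patients and 0.50 x 52 = 26 TSM patients score 100%. A death without admission joins that tied top group.

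**Step 3: size in mean days, by hand.** Assumptions, none from the documents: deaths of 15% versus 5%, death dates uniform over 90 days (mean loss 45 days), 60% admitted, about 9 inpatient days each.

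- Mean inpatient days per patient: 0.60 x 9 = 5.4.
- If death halves a patient's expected inpatient days, the higher-mortality arm gains 0.10 x 0.5 x 5.4 = +0.27 days under A. If death leaves inpatient days unchanged, the gain is 0.
- Under C the same arm also loses 0.10 x 45 = 4.5 days: 0.27 - 4.5 = -4.2.

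Simulations of 3,000 trials on this pattern gave between +0.1 and +0.3 days under A, and about -4.2 under C.

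**Step 4: the Mann-Whitney test itself.** Simulated with 52 per arm, equal underlying hospital use, and a two-sided 0.05 level. That level is borrowed from the SAP's sample-size test ("alpha=0.05, two-tailed"), since none is stated for this outcome. Entries are the percentage of trials significant for / against the higher-mortality arm; where death rates are equal, for one given arm / against it.

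| Assumed pattern | Deaths | A | C |
|---|---|---|---|
| 60% admitted, stays of about 9 days | 15% v 5% | 5.2 / 1.0 | 0.3 / 12.5 |
| 50% of survivors admitted, every death without admission | 5% v 5% | 3.0 / 2.3 | 2.8 / 2.2 |
| same | 10% v 0% | 6.3 / 0.7 | 0.2 / 13.8 |
| same | 15% v 5% | 6.5 / 0.5 | 0.2 / 13.1 |
| same | 20% v 5% | 10.5 / 0.4 | 0.0 / 24.0 |

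Under B, the first row favours the higher-mortality arm in 4.8% of trials. In the other rows B equals A, because no patient who died had inpatient days. A fair test gives about 2.5% on each side.

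**The case against.** A reader might infer that the SAP prescribes a fixed 90-day denominator and deliberately counts days after death as days at home. The documents do not support that. The clause names a 90-day period but no formula, and says nothing of death. The label itself points the other way, since a patient who has died is not at home. The protocol elsewhere prorates for death or divides by time followed, so a days-alive denominator cannot be excluded. This stands, but it does not rescue the outcome: for a death without admission, days alive as denominator also gives 100%.

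A reader might also infer a bias of about four days, or that the result would reverse. That does not follow either. The shift in the outcome as written is 0 to +0.3 days. Nearly all of the -4 is mortality entering a different estimand, one that includes death. It shows what the present measure cannot see, not how far it is biased.

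The stakes are also limited. Table 1 marks only ER use and hospitalizations as primary, the SAP's power statement rests on hospitalization, NYHA class 4 is excluded, and death is recorded in both arms, so an imbalance could be noticed. All of this stands, and it makes the point one of secondary weight.

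**Conclusion.** The gap is real. The definition carries no condition that the patient is alive, no other text supplies one, and on both readings that the wording allows, an early death without admission takes the top rank. This is more than a missing detail, because the formula as given produces a misleading score for such patients.

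The consequence is near-blindness to excess mortality, with at most a slight tilt toward the arm with more deaths. At assumed deaths of 15% versus 5%, significant results in favour of the higher-mortality arm rise from the nominal 2.5% to about 5% to 6.5%. Significant results against it occur in about 1% of trials or fewer, compared with 12.5% to 13.1% if days after death score zero. With equal death rates there is no distortion.

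All death and admission patterns here are assumptions. The documents give no death rate, so the effect in this trial cannot be sized; it is small if deaths are few or balanced. The point concerns a supplementary outcome and does not touch the primary comparisons of hospital and ER use. The SAP should correct it, but the trial's main conclusion does not depend on it.

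**What to change.** Define the outcome as days alive and out of hospital divided by 90, with every day after death counted as zero. Keep the Mann-Whitney test. State how patients lost to follow-up are scored, which the SAP leaves equally open. Report the number of deaths by arm beside the result.

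The cost is a sentence or two of SAP text and a recalculation; the SAP is written in the past tense, so this means recomputing rather than collecting a new outcome. It needs dates of death. Table 1 shows that death is recorded in both arms among the weekly-contact items, but not that the exact date is held, so that must be confirmed.

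The trade-off is that the outcome becomes a composite of hospital use and mortality. Hospital use alone remains available through cumulative LOS. If the sponsor prefers a pure utilization measure, the minimum is to write out the numerator, the denominator and the handling of death, and to avoid presenting the result as patient benefit without the deaths alongside.
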